6.6 Primary Endpoints

Primary endpoints include 1) the percent change from baseline (defined as the average of the 5-7 pain scores obtained in the week prior to enrollment/randomization) in the average daily low back NPRS score during weeks 1-4 and weeks 1-8. The primary analysis will compare the EaseVR group against the VR sham group.

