6.3 Recruitment

The primary and collaborating investigator(s) will identify potential subjects in the Geisinger system who are scheduled for a clinic visit to address their chronic low back pain. These patients will be pre-screened via manual chart review of their electronic health record (EHR) by the research team. Patients meeting the inclusion/exclusion criteria will be called by an IRB-approved study team member (e.g. primary and collaborating physicians, research project coordinator, research assistant) approximately one week prior to their scheduled clinic visit. After hearing a description of the study and completing a short screening assessment, eligible

patients will be asked to report their average lower back pain over the last 24 hours via a Numeric Pain Rating Scale (NPRS) score for 7 days. Each subject will choose how they want to report their daily NPRS scores and will be given the following options: phone calls, texts, or web-based entry via REDCap. They will be instructed to record their scores at the same time each day (\pm 2 hours).

At the end of the 7-day screening period, the study team will assess daily NPRS scores to determine if the subject meets the pain eligibility requirements: (1) subjects must complete at least 5 of 7 daily NPRS scores in the previous 7-day screening period and (2) the overall average NPRS score must remain between 4 and 10 (inclusive) during the screening period. Subjects who are deemed eligible will be approached by a member of the study team during their clinic visit to provide more information about the study and administer informed consent for interested patients.

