6.8 Statistics

A Geisinger statistician will complete the statistics. All statistical analyses will be performed with SAS (SAS 9.4, SAS Institute, Cary, NC), Stata (SE 14.2, StataCorp, LLC, College Station, TX), or R (R 3.5.2, The R Foundation, Vienna, Austria) statistical software, with p-values of <0.05 considered statistically significant.

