6.8.1 Statistical Analysis Plan

We will calculate frequencies for categorical data and means with standard deviations for continuous variables. Bivariate comparisons will be explored using Chi-square or Fisher's exact test for categorical variables and two-sample t-tests or Mann-Whitney tests for continuous variables.

Because pain is expected to decrease over time, and because pain scores may vary by day and time of day administered, we will plan to plot NPRS score vs. time for every patient over the 8-week treatment period, using straight-line interpolation between measurements, which will allow us to use all available measurements (even if some patients recorded more NPRS scores than others) and will avoid placing too much emphasis on a measurement at a single time point (e.g. the 21-day measurement). We will compute a percent-area-under-the-curve (NPRS-%AUC)

measurement where 100% would indicate pain scores of 10 across the entire time period. Each patient will have a different NPRS-%AUC, forming a distribution of measures in each of the two groups, and we will use an unpaired t-test to compare the mean NPRS-%AUC for patients before and after the intervention.

Percent change in PSEQ-2, PCS-4, CPAQ-8, ODI, SF-12 and total opioid usage (measured in MME) will be compared between groups using ANOVA, or, if more appropriate, a nonparametric Kruskal-Wallis test.

Covariates in the analysis of covariance models include study site, sex, duration of pain, opioid use, and baseline outcome scores.

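### The primary NPRS endpoint is percent change, the only NPRS test named is an unadjusted t-test, and the listed ANCOVA is tied to no endpoint

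*Combined protocol and SAP*

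**What the plan says.** Section 6.6 sets the primary endpoint as "the percent change from baseline" in average daily NPRS over weeks 1-4 and weeks 1-8, compared between EaseVRx and sham. Baseline is the "average of the 5-7 pain scores obtained in the week prior to enrollment/randomization". No test is named there.

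Section 6.8.1 takes a different NPRS summary, the percent area under the 8-week pain curve, and states: "we will use an unpaired t-test to compare the mean NPRS-%AUC for patients before and after the intervention". No baseline term is mentioned. Percent changes in PSEQ-2, PCS-4, CPAQ-8, ODI, SF-12 and opioid use "will be compared between groups using ANOVA, or, if more appropriate, a nonparametric Kruskal-Wallis test"; NPRS is not in that list.

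Section 6.8.1 ends: "Covariates in the analysis of covariance models include study site, sex, duration of pain, opioid use, and baseline outcome scores". No endpoint is assigned to these models.

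Section 6.8.2 gives the recruitment target and dropout allowance, but no effect size, SD, correlation or power.

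**The concern.** Three statements bear on the primary comparison and they do not meet. The endpoint in 6.6 has no test, the test in 6.8.1 is attached to another summary, and the one model that would adjust for baseline is attached to nothing.

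The two routes that are tied to NPRS make weak use of the baseline. The t-test ignores it. Percent change divides by it, so the same improvement in points counts differently according to where a patient started, and the ratio generally stays correlated with baseline. Every randomized patient already has this baseline, so the lost precision buys nothing.

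About 100 patients are expected in the analysis, and the Abstract says the results are meant to prepare a larger efficacy trial. An inefficient analysis raises the chance of missing a real effect and widens the estimate passed to that trial. Leaving the choice among three readings open also leaves room to choose after the data are seen.

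**Working it through.** **The plan's own figure.** 100 completers at 20% dropout need 100 / 0.8 = 125 recruits, or 126 for equal arms; 126 × 0.8 = 100.8. The recruitment figure reproduces and gives 50 per arm. There is no stated power to reproduce.

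**Inputs.** From the documents: 50 per arm (6.1, 6.8.2); significance "with p-values of <0.05 considered statistically significant" (6.8); and, for eligibility, "the overall average NPRS score must remain between 4 and 10 (inclusive) during the screening period" (6.3). Assumed: a two-sided test, a 0.5 SD effect, and a baseline-outcome correlation ρ of 0.3 to 0.8.

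**Unadjusted t-test against ANCOVA.** The residual SD is 1 for the unadjusted follow-up mean and √(1 − ρ²) for ANCOVA. Power ≈ Φ(0.5 / (residual SD × √(2/50)) − 1.96). Unadjusted: 0.5 / 0.2 = 2.5, and Φ(0.54) = 70.5%. At ρ = 0.5: 2.5 / 0.866 = 2.887, and Φ(0.927) = 82.3%. The effect detectable with 80% power is (1.96 + 0.84) × 0.2 × residual SD. The equivalent n is 50 × (1 − ρ²), rounded up.

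| Analysis | Residual SD | Power | Gain (points) | Detectable effect (SD) | n per arm matching 50 unadjusted |
|---|---|---|---|---|---|
| Unadjusted | 1.000 | 70.5% | – | 0.560 | 50 |
| ANCOVA, ρ 0.3 | 0.954 | 74.6% | 4.1 | 0.535 | 46 |
| ANCOVA, ρ 0.5 | 0.866 | 82.3% | 11.8 | 0.485 | 38 |
| ANCOVA, ρ 0.6 | 0.800 | 87.8% | 17.3 | 0.448 | 32 |
| ANCOVA, ρ 0.7 | 0.714 | 93.8% | 23.3 | 0.400 | 26 |
| ANCOVA, ρ 0.8 | 0.600 | 98.6% | 28.1 | 0.336 | 18 |

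This is the normal approximation; an exact t calculation lowers each power by less than one point. The gain rises with ρ.

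**The percent-change scale.** With eligible baselines from 4 to 10, a 1-point fall is 1/4 = 25% at baseline 4 and 1/10 = 10% at baseline 10.

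**Percent change against ANCOVA.** There is no closed form, so this was simulated with 50 per arm.

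- *Linear model given the observed baseline, baseline truncated to 4-10, 6,000 trials per setting.* With an additive 0.8-point effect and ρ of 0.3, 0.5, 0.6, 0.7 and 0.8, percent change against ANCOVA was 70.2 v 72.6, 80.6 v 81.8, 85.6 v 87.3, 89.5 v 93.2 and 93.7 v 98.0%. With an effect of 13% of baseline it was 24.3 v 26.2, 66.0 v 70.4, 87.5 v 90.3, 98.3 v 98.9 and about 100 v 100%. The loss is 0 to about 4 points.
- *Latent pain plus day-to-day noise, with follow-up regressing toward the population mean, 4,000 trials per setting (latent SD 1.4, day SD 1.3, 50 diary days).* With an additive 0.8-point effect and ρ 0.4-0.8, percent change had 72-98% and ANCOVA 86-99%, a loss of 1 to 14 points. With the 13% effect and ρ 0.4-0.7 it was 75-95% against 88-98%. A similar run of 2,000 trials per setting showed the loss falling from 6.5-12 points at ρ 0.4 to 0.3-1.8 at ρ 0.8.

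In that last run the loss against the unadjusted t-test moved the other way, from 2.4-3.6 points at ρ 0.4 to 10-15 at ρ 0.8. The two losses therefore cannot be described by one statement about the correlation.

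**The case against.** Baseline-adjusted ANCOVA is in the plan: the closing sentence of 6.8.1 names baseline outcome scores as a covariate. A reader might infer from the t-test that the sponsor left baseline adjustment out altogether, and the documents do not support that. A statistician could fairly read the sentence as covering NPRS, and on that reading much of the loss disappears. What stands is that the sentence assigns the model to no endpoint, while the only test the plan does assign to NPRS is a t-test. The covariate list also includes study site, although 6.1 describes a single-center trial, so it cannot be applied literally.

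The t-test wording is itself unclear. It speaks of patients before and after the intervention, while 6.6 calls for EaseVRx against sham. Treating it as an unadjusted between-arm comparison of follow-up is the reading closest to 6.6, but it is still a reading.

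Percent change is prespecified and easy to interpret, and it matches how Section 5 reports the pilots. It uses the baseline, so its loss may be small. This is also a proof-of-concept study. These points hold, and they bear on how serious the matter is. They do not give a reason to forgo precision that is available from data already collected.

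**Conclusion.** The point stands as a problem of efficiency and specification. The endpoint in 6.6, the t-test and the unassigned ANCOVA in 6.8.1 need to be reconciled, and assigning the ANCOVA to NPRS is the better choice.

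Against the unadjusted t-test, the closed form gives a loss of about 4 to 28 power points for ρ from 0.3 to 0.8, larger at higher correlation. Against percent change, the simulations give about 0 to 14 points, generally larger at low correlation where follow-up regresses to the mean. ANCOVA was never materially worse in any setting tried.

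Three stronger conclusions are tempting and not supported:

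- That the planned test is invalid. Under randomization neither route invalidates the between-arm comparison.
- That this trial loses a known amount of power. The effect size, SDs, correlations and number of diary days are all assumed, and the results are sensitive to them.
- That the loss always grows as the correlation falls. This applies to percent change in some models; against the t-test the reverse holds.

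**What to change.** In 6.6 and 6.8.1, state one primary analysis: a between-arm (EaseVRx against sham) ANCOVA of mean daily NPRS, or of NPRS-%AUC, over weeks 1-8, with the mean of the 5-7 pre-randomization scores as covariate. It replaces the unpaired t-test and its before-and-after wording. Say what role the weeks 1-4 result keeps. State which endpoints the ANCOVA sentence covers, and remove study site from its covariates or explain it.

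Report percent change descriptively, for example as the adjusted difference divided by mean baseline.

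The cost is wording. No new data, visits or patients are needed. It is more than an SAP edit, though: the endpoint definition in 6.6 changes, and with it the quantity being estimated, so the change should be made and documented before unblinding.

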Access to interdisciplinary chronic pain management programs is seriously lacking in the United States. In 1999, it was estimated that there were over 1000 interdisciplinary pain management programs in the United States¹⁶. This number has dropped dramatically to 150 in 2011¹⁷. Based on the number suffering from chronic pain, this data suggests there is approximately one interdisciplinary program for every 670,000 chronic pain victims in the United States. EaseVRx is a simple, low-risk, non-invasive device with the potential to become a ubiquitous pain management therapy to address the lack of access to interdisciplinary care. In view of the complex nature of chronic pain, treatment often necessitates use of a blend of different approaches with a focus on maximizing symptom relief so that patients are able to lead the highest quality of life possible.

This study will evaluate the degree and duration of analgesic effect on chronic low back pain from use of the EaseVRx device. To control for any potential placebo therapeutic effect that may be experienced merely by donning a VR headset, a sham VR control group is included in the study design. The VR sham product will consist of a void theater, which is defined as a 2D virtual screen in front of the user that displays a variety of video content. The screen will be surrounded by a solid black environment to minimize immersion. The user experience is best described as being inside of a pitch black movie theater. The content displayed in the void theater will be a variety of 2D nature-related content that is not intended to have therapeutic effect. The VR sham user interface and functionality will be designed to mirror the user interface and functionality of the EaseVRx intervention.

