4 HYPOTHESIS AND SPECIFIC AIMS

4.1 Primary Aim 1

Compare pain and pain coping skills among the VR sham and the EaseVRx group. *Hypothesis: Chronic low back pain patients randomized to the EaseVRx approach who use the device in accordance with the treatment protocol will have significantly decreased pain scores and improved pain coping skills 4, 8, and 12 weeks after starting the 8-week VR treatment.*

4.2 Secondary Aim 1

Compare physical function as measured by the Oswestry Disability Index (ODI) among the VR sham and EaseVRx group. *Hypothesis: Chronic pain patients randomized to the EaseVRx approach who use the device in accordance with the treatment protocol will have significantly better physical function (i.e. lower ODI scores) 4, 8, and 12 weeks after starting the 8-week VR treatment.*

4.3 Secondary Aim 2

Compare analgesic medication use among the VR sham and EaseVRx group. *Hypothesis: Chronic pain patients randomized to the EaseVRx approach who use the device in accordance with the treatment protocol will have decreased utilization of opioid and non-opioid pharmacotherapy 4, 8, and 12 weeks after starting the 8-week VR treatment.*

4.4 Secondary Aim 3

To assess the feasibility of EaseVRx as a self-administered, home-based approach to chronic pain management, in terms of patient compliance, program retention, patient satisfaction, and safety. *Hypothesis: EaseVRx will be a feasible approach to chronic pain management, with high rates of patient compliance, retention, and satisfaction among chronic pain patients after completing an 8-week course of treatment with EaseVRx.*

4.5 Secondary Aim 4

Compare healthcare cost and utilization among the VR sham and EaseVRx group among patients with Geisinger Health Plan as their primary insurance. *Hypothesis: Chronic pain patients randomized to the EaseVRx approach who use the device in accordance with the treatment protocol will have significantly lower costs and utilization (i.e. office visits, therapy sessions, inpatient/ED admissions) 3 months, 6 months, and 12 months after starting the 8-week VR treatment.*

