6.5.1 Study Time and Events Table

Study Procedures	Day 0 (baseline visit)	Daily for 8 weeks*	4 weeks*	8 weeks*	12 weeks*	6 and 12 months**
Physical examination (office visit)	X					
Review inclusion/exclusion	X					
Demographics, medical history	X					
Informed consent	X					
Randomization	X					
User instructions	X					
NPRS pain score	X	X	X	X	X	
PSEQ-2, PCS-4, CPAQ-8, ODI, SF-12	X		X	X	X	
Program satisfaction questions				X		
Analgesic drug use	X	X	X	X	X	X
Utilization and cost					X	X
Device utilization statistics ¹		X				
AE / Complication Reporting	X	X	X			

¹ EaseVRx and sham VR groups only

* Data collected from patient at home via phone or online; not an in-person visit

** Retrospective review only

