6.7 Secondary Endpoints

Secondary outcome measures include:

- Average daily minutes of VR or sham use at during weeks 1-4 and weeks 1-8.
- Number of days VR or sham used.
- Number of days that participants completed all outcome assessments.
- Patient satisfaction score (min 3 – max 12).
- Likelihood of recommending VR treatment to someone else (min 1 – 10 max).
- Number of adverse events related to the study treatment.
- Change from baseline PSEQ-2, PCS-4, CPAQ-8, SF-12 score at 4, 8, and 12 weeks.
- Change from baseline in total ODI score as well as subscale scores at 4, 8, and 12 weeks.
- Average self-reported daily amount of analgesic medication used during weeks 1-4 and weeks 1-8.
- Total milligrams of morphine equivalent doses filled from PDMP database at 3 months, 6 months, and 12 months.
- Total number of office visits, admissions, emergency room visits, and therapy sessions related to the patient's lower back pain at 3 months, 6 months, and 12 months.
- Total cost of care related to patient's lower back pain at 3 months, 6 months, and 12 months.

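### Two nested primary pain windows have no decisive window or success rule, and the 12-week pain hypothesis in Primary Aim 1 has no endpoint or specified analysis

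*Combined protocol and SAP*

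**What the plan says.** - **Primary endpoints (section 6.6).** Percent change from baseline "in the average daily low back NPRS score during weeks 1-4 and weeks 1-8", with EaseVRx compared against sham. Baseline is the mean of the 5 to 7 scores from the week before enrolment.
- **Significance (section 6.8).** All analyses are run "with p-values of <0.05 considered statistically significant". No sidedness, testing order or multiplicity adjustment is given.
- **Pain analysis (section 6.8.1).** The plan says "we will plan to plot NPRS score vs. time for every patient over the 8-week treatment period". It then computes an NPRS-%AUC on which 100% means a score of 10 throughout, and uses an unpaired t-test "to compare the mean NPRS-%AUC for patients before and after the intervention". The following sentence, on between-group percent change, names the coping scales, ODI, SF-12 and opioid use, but not NPRS.
- **Primary Aim 1 (section 4.1).** The hypothesis is "significantly decreased pain scores and improved pain coping skills 4, 8, and 12 weeks after starting the 8-week VR treatment".
- **Secondary endpoints (section 6.7).** The coping scales appear here: "Change from baseline PSEQ-2, PCS-4, CPAQ-8, SF-12 score at 4, 8, and 12 weeks". NPRS does not.
- **Schedule (section 6.5.1).** The row "NPRS pain score" is marked at baseline, daily for 8 weeks, and at 4, 8 and 12 weeks.
- **Stated purpose (section 3.2).** "This study will evaluate the degree and duration of analgesic effect on chronic low back pain".

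**The concern.** The weeks 1-4 window lies inside the weeks 1-8 window, so the two results will usually agree, but they need not. An early effect that fades, or one that builds late, could make one window significant and the other not. The plan does not say what the primary conclusion would then be. A rule chosen after the data are seen could be either-wins, both-must-win, or whichever window looks better, and these rules have different error rates.

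The aim and the endpoints also disagree. Aim 1 treats coping skills as primary while section 6.7 treats them as secondary. Aim 1 predicts lower pain at 12 weeks, which is 4 weeks after the device programme ends, but the primary windows stop at week 8 and no secondary endpoint continues the pain score. The durability of pain relief would be measured and then left without a planned answer.

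**Working it through.** **The plan's own figure.** The sample-size section (6.8.2) gives only recruitment: 126 patients, 20% dropout, 100 analysed. With 50 per arm, 50 / 0.8 = 62.5, rounded up to 63, and 2 × 63 = 126. This reproduces. No power, effect size, SD or familywise error rate is stated, so there is nothing further to reproduce.

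**Correlation between the two windows.** Let A be a patient's percent change for weeks 1-4 and B the percent change for weeks 5-8. Both use the same baseline. With complete diaries, the weeks 1-8 result is W = (A + B)/2. With equal SDs σ and corr(A, B) = r:

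- Cov(A, W) = σ²(1 + r)/2
- Var(W) = σ²(1 + r)/2
- corr(A, W) = √((1 + r)/2)

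**Error rates.** Take the two test statistics as bivariate normal with that correlation, no effect in either window, and two-sided 0.05 (|z| > 1.96; sidedness is assumed). Then P(either) = 1 − P(both |z| ≤ 1.96), and P(both) = 0.05 + 0.05 − P(either).

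| r (assumed) | corr(A, W) | Either wins | Both win |
|---|---|---|---|
| 0.3 | 0.806 | 7.8% | 2.2% |
| 0.5 | 0.866 | 7.3% | 2.7% |
| 0.7 | 0.922 | 6.8% | 3.2% |
| 0.9 | 0.975 | 6.0% | 4.0% |

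For example, at r = 0.5 the either-wins value is 0.0734, so both-win is 0.10 − 0.0734 = 0.0266. At r = 0 the either-wins value would be 8.3%. Two independent tests would give 1 − 0.95² = 9.75%, which nested windows do not reach when r is zero or above. Both-must-win cannot exceed 5%, because each test alone has level 5%.

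**Does section 6.8.1 choose a window?** Set against section 6.6:

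| | Section 6.6 | Section 6.8.1 pain test |
|---|---|---|
| Measure | Percent change from baseline | NPRS-%AUC, a level scaled to a score of 10 |
| Period | Weeks 1-4 and weeks 1-8 | 8 weeks |
| Contrast | EaseVRx versus sham | Worded as before versus after |
| Called primary | Yes | No |

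The weeks 1-4 window therefore has no named test, and the weeks 1-8 window has only a mismatched one.

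**Is 12-week pain an endpoint?** Section 6.7 has 12 entries: use per day, days used, days with complete assessments, satisfaction, likelihood of recommending, adverse events, coping scales with SF-12, ODI, self-reported analgesics, filled morphine equivalents, utilisation and cost. None uses NPRS. The 12-week ODI and SF-12 do not fill the gap, since section 6.5 assigns them to physical function and quality of life and assigns pain to NPRS.

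**The case against.** Several points on the other side are fair.

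- **Between-arm intent.** The sentence on the t-test also refers to a distribution of measures in each of the two groups, and section 6.6 says that the primary analysis compares the arms. The before-and-after wording may well be a slip. That stands, but correcting it would still leave a different measure and no choice of window.
- **Generic analyses.** Section 6.8.1 also mentions exploratory two-sample comparisons, and covariance models that include baseline scores. These could be stretched to cover NPRS, including at 12 weeks. They name neither, so they do not specify the analysis.
- **A both-required reading.** Section 6.6 joins the windows with an *and*, and Aim 1 lists its time points together. Requiring both is a natural reading and would keep the error at or below 5%. The plan does not state it, and a list of windows is not a success rule.
- **Pilot status.** The abstract describes proof-of-concept work ahead of a larger trial, so strict error control matters less. This is why the inflation should not be overstated. The protocol nonetheless names primary endpoints, hypothesises significance and sets a threshold, and planning the next trial needs a clear reading.
- **Open-ended list.** Section 6.6 opens with an item 1) and has no item 2), so the list may be unfinished. That is a reason to complete it.
- **Duration.** The statement of purpose in section 3.2 names no 12-week point. The 12-week claim rests on Aim 1 and on the schedule.
- **Other remedies.** Requiring both windows would also control error, and removing 12-week pain from Aim 1 would also restore consistency. The choice between them is a design preference; leaving it open is not.

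**Conclusion.** The concern holds. As written, the plan cannot say whether the primary result is positive when the two windows disagree, and it contains no endpoint or named analysis for the 12-week pain hypothesis in its own primary aim.

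The numerical inflation is modest and conditional: 6.0% to 7.3% if a win in either window counts, and 2.7% to 4.0% with no effect in either window if both must win. These figures assume r between 0.5 and 0.9, equal SDs, complete diaries and two-sided tests. The documents give no value for r. The larger harm is the freedom to choose the rule after seeing the data. The coping-skills mismatch is a lesser inconsistency, since those scales do have a defined secondary endpoint. The matter should be corrected, but it does not undermine the trial's design or data collection.

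**What to change.** 1. In section 6.6, make percent change in average daily NPRS over weeks 1-8 the single primary endpoint, at two-sided 0.05. This matches the length of the programme and the period in section 6.8.1.
2. In section 6.8.1, make the pain test analyse that endpoint between arms, and remove the before-and-after wording.
3. Test weeks 1-4 next in fixed sequence, only if weeks 1-8 is significant. This holds the familywise error at or below 5% with recruitment unchanged at 126.
4. In section 6.7, add the between-arm change from baseline in NPRS at 12 weeks as a secondary endpoint, using the score already scheduled, and name its analysis in section 6.8.1.
5. Move coping skills from Primary Aim 1 to a secondary aim. Keep the existing secondary endpoints as secondary.

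The cost is protocol and SAP wording, with no new data collection. There are two downsides: weeks 1-4 becomes confirmatory only if weeks 1-8 succeeds, and a single 12-week score is noisier than an average of daily scores.
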